7.0 Study Design and Procedures

7.1 Study Design

Any adult patient scheduled for routine CTA meeting the inclusion/exclusion criteria and providing consent will be included in the study. The patient will be administered a low dose of intravenous contrast based on the study examination as described below. The contrast agent being used is Omnipaque. The scan will be performed under the supervision of the primary investigator or the described team members to make sure that the study is of diagnostic quality.

The following dose protocols will be followed:

CTA of the chest: 40 mL of intravenous contrast at a rate of 5mL/sec. A region of interest (ROI) to trigger the scan will be placed in the aortic arch. If scan is performed using high pitch helical mode, the scan delay will be increased by 2 seconds.

CTA of the abdomen OR or CTA of the chest and abdomen or CTA of the abdomen and pelvis or CTA of the chest, abdomen and pelvis: 50 mL of intravenous contrast at a rate 5mL/sec. A region of interest (ROI) to trigger the scan will be placed in the aortic arch. If scan is performed using high pitch helical mode, the scan delay will be increased by 2 seconds.

All other imaging parameters will remain unchanged, given that the subjects enrolled will be clinical patients of the principle investigator.

Following the examination, the primary investigator (PI) or team members will evaluate the images obtained with low contrast dose and each patient's prior CTA examination performed with routine contrast dose. This will be done by quantitative and qualitative measures. For the quantitative portion, the PI or team members will place regions of interest on predetermined arterial locations to obtain measure the degree of opacification. For qualitative measurement, the images will be presented in a blind fashion to two thoracic trained board certified radiologists and a board certified interventional radiologist to determine the quality of the images based on a Likert numerical scale. Qualitative and quantitative data for the images obtained with low contrast dose and those for the prior CTA examinations performed with routine contrast dose will be compared. This data along with details of the

scan protocol (dose, dose rate, scanning parameters etc.) and demographic data (such as sex, age and BMI at the time of examination) will be recorded in Redcap.

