3.0 Inclusion and Exclusion Criteria

3.1 Inclusion Criteria

- 1. Any adult patient scheduled for a computed tomographic arteriogram (CTA) of the chest or CTA of the abdomen or CTA of the chest and abdomen or CTA of the abdomen and pelvis or CTA of the chest, abdomen and pelvis who had undergone a prior CTA of the same region performed with the standard contrast dose (100 mL) at this institution will be included in the study.
- 2. The follow-up scan will be routine standard of care, no emergency imaging patient will be approached for this research.

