7.2 Study Procedures

7.2.1 Clinic Visit

The process of obtaining the CTA images will be unchanged from the patient's standpoint. One difference will be that the examination will be supervised by a team member. The intravenous contrast dose administered will be decreased according to the parameters written above. If the study is deemed non-diagnostic at the time of scanning, the study will be repeated. The standard of care at this institution in the setting of a non-diagnostic study is to repeat the study with a 75mL dose of contrast, for a total of 175mL of contrast. Given that the dose of contrast that will be administered for this study (40-50mL) is below the routine amount (100mL). Performing a repeat study with 75mL of intravenous contrast will not exceed the contrast dose that would have been normally administered.

7.2.2 EXAMPLE: Visit 2 or Day 2 or Post-test, etc. (format accordingly) Not Applicable

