8.2 Sample size determination

This number of patients achieves 80% power, with a 7.5% equivalence margin, at a 5% significance level using a two-sided equivalence test of correlated proportions when the actual difference of the proportions is zero.

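### Section 7.1 blinds the Likert reads but states no masking for the opacification ROIs, although scan-date order identifies the dose

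*Combined protocol and SAP*

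**What the plan says.** Section 7.1 (Study Design) describes two measurements on each pair of scans.

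- **Quantitative:** "the PI or team members will place regions of interest on predetermined arterial locations", to measure opacification. Nothing is said about what the measurer may see.
- **Qualitative:** "the images will be presented in a blind fashion to two thoracic trained board certified radiologists" and an interventional radiologist, "to determine the quality of the images based on a Likert numerical scale".

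The team that places the ROIs is also the team at the scanner: "The scan will be performed under the supervision of the primary investigator or the described team members". Section 7.2.1 repeats this: "One difference will be that the examination will be supervised by a team member".

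The comparator is each patient's "prior CTA examination performed with routine contrast dose", and Section 3.1 requires that scan to have been done at 100 mL. Section 7.4.3 marks assignment to groups as not applicable.

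Section 8.3 analyses the measured data with paired t-tests. Section 8.2 sizes the trial "using a two-sided equivalence test of correlated proportions when the actual difference of the proportions is zero". Section 10.7 refers to both.

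**The concern.** The plan protects one half of its comparison from knowledge of dose and is silent on the other half. Dose and time order are completely tied in this design, so anyone who can see the two scan dates knows which is the low-dose study, whether or not they attended it.

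The room for bias lies in how an ROI is placed at a named site. Its size, its exact level, and how it avoids vessel wall, calcification or mixing artefact are not specified. If those choices differ with known dose, even slightly, the difference is systematic and recruiting more pairs does not remove it. Sections 1.1 and 1.2 aim to show no difference, so a shift that hides a loss would favour the hoped-for result. A shift the other way would produce a difference that is not real.

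**Working it through.** **Is the measurer masked anywhere?**

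1. Section 7.1 attaches blinding to the Likert reads only.
2. Section 7.4.5 marks blinding as not applicable, but it concerns the contrast agent and so neither masks nor unmasks the person placing ROIs.
3. Section 6.2.1.2 mentions a linking list, and Section 9.1.1.1 refers coding to a separate data-plan form. Both concern confidentiality.
4. No other section addresses the ROI measurer.

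**Does date order give the dose?** Section 3.1 fixes the prior scan at 100 mL. Sections 7.1 and 7.4.2 fix the study scan at 40 or 50 mL. There is no randomised order. The later scan of each pair is therefore always the low-dose one. A same-day repeat of a non-diagnostic scan (Section 7.2.1) does not change this, because the prior scan still has the earlier date.

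**The plan's own figure.** Section 8.2 gives 180 subjects for 80% power and a 7.5% margin, but not the discordant proportion p. With two one-sided 5% tests and a true difference of zero, n = (1.645 + 1.282)² × p / 0.075². Setting n = 180 gives p ≈ 0.118; with 2.5% per side it gives p ≈ 0.096. The figure can be neither confirmed nor refuted, and nothing here depends on it. Only n = 180 is carried forward.

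**How much would a placement shift matter?** The documents give no bias size, paired SD or expected HU loss, so the following is an illustration under assumed values.

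- Standard error of the mean paired difference = 1/√180 = 0.0745 SD.
- A two-sided 5% paired t-test with 179 degrees of freedom (noncentral t) has 80% power at a true loss of 0.210 SD.
- If the shift hides loss, power is evaluated at 0.210 minus the shift. If there is no true difference, the rejection rate is evaluated at the shift itself.

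| Assumed shift (SD) | Share of 0.210 SD | Power if it hides loss | False positives if no true difference |
|---|---|---|---|
| 0 | 0% | 80% | 5% |
| 0.02 | 10% | 71.7% | 5.8% |
| 0.05 | 24% | 56.9% | 10.2% |
| 0.10 | 48% | 31.1% | 26.6% |

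Simulation with 40,000 trials per case gave 71.8%, 57.1% and 30.9% for power, and 5.8%, 10.1% and 26.6% for false positives.

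In HU, with an assumed paired SD of 30, 60 or 90, a shift of 0.02 SD is 0.6, 1.2 or 1.8 HU. A shift of 0.05 SD is 1.5, 3.0 or 4.5 HU, and 0.10 SD is 3, 6 or 9 HU.

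**The case against.** The strongest reply has four parts.

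- **Silence is not unmasking.** The protocol never says that measurers see dates or doses, nor that one person both supervises and measures the same patient. This stands, so the point about dates is conditional on their being visible. Still, a protocol that specifies blinding for one measurement and not for the other gives staff no instruction to mask the second.
- **HU is objective and the sites are chosen in advance.** This also stands and limits the scope for bias. The word used for the sites may even fix the level, but the text does not say so, and it gives no ROI size or artefact rule.
- **HU may be only supportive.** The endpoint in Section 1.2 is image quality, which the blinded readers score, and Section 8.2 is built on proportions, which HU does not yield without a cut-off. This is a fair reading, though Sections 8.3 and 10.7 leave it open. If it is right, the concern is confined to the quantitative comparison.
- **The bias sizes are assumed.** They are. The 0.21 SD loss is back-solved from 180 pairs, and nothing in the documents shows that ROI placement would shift HU by these amounts. The table shows how sensitive the test is, not what will happen.

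**Conclusion.** The concern holds. Masking is stated for the Likert reads and for nothing else. ROIs are placed by the pool that supervises the low-dose scans, and scan-date order identifies the dose.

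The size of any bias is unknown. If it were 0.02 to 0.10 SD with 180 pairs, power for a 0.21 SD loss would fall from 80% to between 72% and 31%, or false positives would rise from 5% to between 6% and 27%. How far this reaches the trial's main conclusion depends on whether HU is primary or supportive, which the documents do not settle. The change should be made, because it improves a planned comparison at little cost; confidence in its practical importance is moderate.

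**What to change.** Add to Section 7.1:

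> ROIs will be placed by the study team on images stripped of identifiers, scan date and contrast dose, coded and shown in random order. Dose will be linked to the measurements only afterwards. ROI size, the level at each arterial site, and rules for avoiding vessel wall, calcification and mixing artefact will be fixed in writing before the first measurement.

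Having ROIs placed by a member who did not supervise that scan is optional, where one is available. Supervision at the scanner stays as written.

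The cost is image preparation and slightly slower measurement by the existing team, over at least 2 × 180 = 360 examinations. Much of this preparation is already needed to show the images blind to the radiologists. No patients, visits or scans are added. Masking will be incomplete where the enhancement itself reveals the dose; there, the fixed ROI rules still limit discretion.

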7.2 Study Procedures

7.2.1 Clinic Visit

The process of obtaining the CTA images will be unchanged from the patient's standpoint. One difference will be that the examination will be supervised by a team member. The intravenous contrast dose administered will be decreased according to the parameters written above. If the study is deemed non-diagnostic at the time of scanning, the study will be repeated. The standard of care at this institution in the setting of a non-diagnostic study is to repeat the study with a 75mL dose of contrast, for a total of 175mL of contrast. Given that the dose of contrast that will be administered for this study (40-50mL) is below the routine amount (100mL). Performing a repeat study with 75mL of intravenous contrast will not exceed the contrast dose that would have been normally administered.

7.2.2 EXAMPLE: Visit 2 or Day 2 or Post-test, etc. (format accordingly) Not Applicable

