1.2 Primary Study Endpoints

The objective is to prospectively evaluate image quality of CTA examinations performed with an ultralow contrast dose protocol. The primary endpoint would be to show that there is no statistical difference in the quality of the images.

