1.3 Secondary Study Endpoints

Not Applicable

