2.2 Previous Data

A small number of patients have been imaged with a decreased contrast dose (up to 60% less contrast volume). By taking advantage of scanner speed and number of detectors, a smaller overall dose can be given while still obtaining adequate diagnostic imaging. Quantitative measurements of vascular enhancement (in Hounsfield units) at select locations show no differences in vascular opacification. In addition, qualitative evaluation of these images by board certified diagnostic radiologists show no difference in image quality between examinations performed with reduced contrast dose versus examinations performed with standard contrast dose. This data suggests that the same quality of images can be obtained with a lower dose of contrast minimizing the risk of contrast induced nephropathy. No references are available at this time regarding the rate of re-imaging due to non-interpretable CTA studies. In correspondence with several CT technologists, they stated that in their experience, rarely does a CTA of the chest or chest, abdomen and pelvis have to be repeated

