7.4.2 Treatment Regimen

At this institution, CTAs are performed with the standard contrast dose of 100 mL. This study will administer intravenous contrast, Omnipaque, at a dosage of 40 mL at a rate of 5mL/sec or at 50 mL at a rate of 5mL/sec as described above.

- 7.4.3 Method for Assigning Subject to Treatment Groups Not Applicable
- 7.4.4 Subject Compliance Monitoring Not Applicable
- 7.4.5 Blinding of the Test Article Not Applicable

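### A low-dose scan that fails and is repeated is not an outcome in any endpoint or analysis, so a low to moderate failure rate can pass unmeasured

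*Combined protocol and SAP*

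**What the plan says.** - **Repeat scans.** Section 7.2.1: "If the study is deemed non-diagnostic at the time of scanning, the study will be repeated". The repeat volume discussed there is 75 mL, which is not the regimen under test. Section 7.4.2 gives that regimen as "at a dosage of 40 mL at a rate of 5mL/sec or at 50 mL at a rate of 5mL/sec".
- **Endpoints.** Section 1.2: "The primary endpoint would be to show that there is no statistical difference in the quality of the images". The section headed "1.3 Secondary Study Endpoints" is marked not applicable.
- **Comparison.** Section 7.1 compares "Qualitative and quantitative data for the images obtained with low contrast dose and those for the prior CTA examinations performed with routine contrast dose". It does not mention repeated scans.
- **Analysis.** Section 8.3 plans paired t-tests on each patient's two examinations. It gives no analysis set and no rule for repeats. Section 8.2 sizes the trial "using a two-sided equivalence test of correlated proportions when the actual difference of the proportions is zero", with a 7.5% margin, but does not say what event the proportion counts.
- **Repeat rate.** Section 2.2 concedes: "No references are available at this time regarding the rate of re-imaging due to non-interpretable CTA studies". It adds only the technologists' impression that repeats are rare. Section 10.1 asks for the number of repeats among the first 20 patients, as part of a safety summary for the IRB. No later count is planned.

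**The concern.** The trial asks whether contrast volume can fall without loss of image quality. A scan that has to be repeated on the table is direct evidence on that question, and section 11.0 names the extra radiation as a risk. Because success means finding no difference, anything that dilutes or removes failed scans pushes the result towards success. As written, the trial could report no difference without estimating how often the reduced volume led to a second scan, although section 2.2 says that no reference gives this rate.

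**Working it through.** **Inputs from the documents.** n = 180 (8.1); 80% power, 7.5% margin, 5% level, true difference zero (8.2); paired t-test (8.3). The documents give no repeat rate, SD, Likert range or discordance, so these are assumed or back-solved below.

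**1. The plan's own figure.** For a paired-proportion equivalence test (two one-sided tests), n = pd × (z₁₋α + z₁₋β/₂)² / margin², where pd is the proportion of discordant pairs. Since pd is not stated, 180 can only be solved backwards:
- 5% per side: pd = 180 × 0.075² / (1.645 + 1.282)² = 0.118
- 2.5% per side: pd = 180 × 0.075² / (1.960 + 1.282)² = 0.096

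The margin corresponds to 0.075 × 180 = 13.5 patients.

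**2. Failed scan kept and read (the plain reading).** Suppose a failed scan loses L = 2 or 3 Likert points, the paired SD is otherwise 0.8-1.2, and the other scans do not differ. At repeat rate r the mean shift is rL and the SD becomes √(SD² + L²r(1−r)). At r = 5% (9 patients):
- L = 2, SD = 1.2: shift 0.10; SE = √(1.44 + 0.19)/√180 = 0.095; ratio 1.05; non-significant in about 82% of trials.
- L = 3, SD = 0.8: shift 0.15; SE = √(0.64 + 0.4275)/√180 = 0.077; ratio 1.95; non-significant in about 51%.

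Simulation over the whole grid (two-sided paired t-test at 5%):

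| Repeat rate | t-test non-significant |
|---|---|
| 3% | 77-90% |
| 5% | 51-82% |
| 8% | 18-64% |
| 10% | 7-49% |

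So at 10% the test is significant in 51-93% of trials.

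**3. Failed patients left out (not planned, but not barred).** Assume that the section 8.2 proportion means diagnostic adequacy, that the prior scan was adequate in every repeated patient, and that background discordance is 11.8%, split equally. Exact enumeration of a Wald equivalence test at 5% per side, with 7.5% excess failures (a true loss equal to the margin), gives:
- failures counted: equivalence declared 5% of the time;
- failures excluded (about 13-14 patients): 70-76%. The range depends on whether 13 or 14 patients are removed and on how the background discordance is spread over those remaining.

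At 2.5% per side with 9.6% discordance, the figures are about 3% and 74%.

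**4. What the first-20 count can show.** At a true rate of 5%, P(0 or 1 repeat in 20) = 0.95²⁰ + 20 × 0.05 × 0.95¹⁹ = 0.74. A count of 0/20 has an exact 95% CI of 0-17%. A full-trial count of 9/180 would give 2.3-9.3%.

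**The case against.** The strongest reply is that retention is already settled. Section 7.1 includes every eligible, consenting patient and evaluates the low-dose images. Section 8.3 analyses each patient. Section 3.3.1 lists no ground for removal except the patient declining or withdrawing. Most of this stands. A reader might infer that the plan drops failed patients, or lets the 75 mL repeat stand in as low-dose data; the documents support neither. The exclusion figures in step 3 therefore describe a departure that the text does not forbid, and not the plan itself. What remains is that no sentence applies the rule to repeated scans.

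Second, 3% and 5% failure lie inside a 7.5% margin if that margin is read as diagnostic adequacy, so not rejecting there need not be a wrong conclusion. That is fair. But the plan attaches the margin to no defined event, and at 8%, above the margin, the t-test still misses the loss in 18-64% of trials. Step 2 also overlaps with the mismatch between equivalence sizing and t-test, which is a separate point. It models the Likert score only; the arterial opacification measurements might register some failures.

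Third, a repeat is not pure dose failure. Section 11.0 says that non-diagnostic scans also occur at the standard volume, and the on-table judgement is made by staff who know the dose. This stands, and it shapes the fix.

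Fourth, the first-20 look is a safety check and not an estimator. Section 10.6 adds weekly cumulative review, and section 7.1 records details of the "scan protocol (dose, dose rate, scanning parameters etc.) and demographic data", so a full count is probably recoverable. True, but no section plans to report one.

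A reader might also infer a gap over which of two prior 100 mL acquisitions to use, because section 11.0 allows a second standard dose. Section 7.2.1 gives 75 mL as the institution's usual repeat volume, so this would seldom arise and is not pressed.

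**Conclusion.** The concern holds in a limited form. It is certain from the text that a repeat is not an outcome in any endpoint or analysis and that its full-trial rate is not a planned estimate. The plain reading keeps the failed scan in the comparison, so the main consequence is dilution and not exclusion: failure rates of 3-5% would usually go unnoticed by the t-test, and rates near 10% would usually be seen. Those sizes rest on assumed score losses and SDs. The contrast of 5% with 70-76% applies only if failed patients were left out, and it depends further on the back-solved discordance and on reading the undefined proportion as adequacy. How much this matters in practice depends on a repeat rate that the documents do not give. It should be put right before analysis, but it does not by itself invalidate the design.

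**What to change.** 1. State in 7.1 and 8.3 that the first 40-50 mL acquisition is the one read and measured, and that no patient is dropped because of a repeat.
2. Define the section 8.2 paired proportion as diagnostically adequate on first acquisition, and test it against the stated 7.5% margin.
3. Apply one failure rule to both scans. Either any recorded repeat of the low-dose scan or of the prior 100 mL scan, at whatever repeat volume, counts as not adequate; or the blinded readers' adequacy rating of the first acquisition is used for both. Name one as primary and the other as a sensitivity analysis.
4. Report the low-dose repeat rate in all patients with a 95% CI, and the recorded reason for each repeat.

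**Cost.** One repeat field with its reason in REDCap, a check of prior records for repeats, and the binary endpoint and its test written into 8.3. The chance of declaring equivalence falls if excess repeats occur: with 11.8% background discordance it is about 79%, 72%, 60% and 45% at 0%, 1%, 2% and 3% excess repeats. With 4-8% background discordance it is 58-73% at 3%. No dose or repeat-scan rule is changed.

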2.0 Background

2.1 Scientific Background and Gaps

Currently, at our institution, routine CTA examinations are obtained with a dose of 100mL of intravenous contrast. In the setting of renal dysfunction, this dose is reduced to 75mL to minimize the risk of contrast induced nephropathy. This dose can be further adjusted giving some flexibility depending on the BMI of the patient and type of scanner used. Given the recent advancements of computed tomography hardware, the scanning speed has greatly increased allowing for reduction in contrast dose. However, at our institution, the dosage and administration rate of intravenous contrast has not yet been adjusted to take advantage of improvements in scanning hardware.

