2.3 Study Rationale

CTA is the imaging of choice for the evaluation of the aorta. Aortic CTAs are performed for evaluation of acute aortic syndromes, vasculitidies, as well as chronic conditions such as aortic aneurysms and congenital anomalies. Examinations are performed for pre-operative evaluation and post-operative follow up in many of these patients. This patient population includes patients with many comorbidities, such as hypertension and diabetes, as well as elderly patients. All these conditions contribute to renal dysfunction. For this reason, the radiology department at this institution has a policy to evaluate renal function before a contrast enhanced CT scan in the setting of increased age (>60 years), history of renal dysfunction or diabetes. Decreasing the contrast dose is important to prevent further damage to the kidneys by contrast induced nephropathy (CIN). It is thought that reducing the contrast dose will reduce

the risk of nephropathy. Development of a low dose protocol would potentially decrease the risk of contrast induced nephropathy in this patient population.

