3.2 Exclusion Criteria

- 1. Patients with no prior CTA imaging for comparison.
- 2. Any pediatric patient (age <18).
- 3. BMI >40
- 4. Inability to follow instructions.
- 5. Allergy to intravenous contrast.
- 6. GFR less than 60 mL/min/1.73 m²⁻GFR should be within normal range. This would allow a repeat study if needed and not pose an increased risk to renal dysfunction.
- 7. Cognitively Impaired Adults
- 8. non-English speaking patients
- 9. Pregnant Females
- 10. Endoleak studies decreased contrast makes evaluation of an endoleak difficult on delayed imaging.

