4.0 Recruitment Methods

4.1 Identification of subjects

Medical records of adult patients scheduled for a routine computed tomography arteriogram will be evaluated prior to CTA imaging to identify subjects meeting the inclusion/exclusion criteria.

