4.2 Recruitment process

Patients scheduled for routine CTA examinations will be screened, via medical records, to find out if they have had a prior CTA of the aorta with routine dose of intravenous contrast within the past two years. Those patients within this group that meet inclusion criteria and do not have any exclusion criteria will be offered to participate in the study.

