5.0 Consent Process and Documentation

5.1 Consent Process

5.1.1 Obtaining Informed Consent

5.1.1.1 Timing and Location of Consent

Informed consent will be obtained prior to examination in the IV preparation room or scanner room.

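### Does the 75 mL repeat scan lack a renal safeguard because no section says where each subject's GFR comes from?

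*Combined protocol and SAP*

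**What the plan says.** Section 7.1 sets the study dose at 40 mL for a chest CTA and 50 mL for the other regions. Section 7.2.1 describes the institution's usual response to a non-diagnostic scan, a 75 mL repeat giving 175 mL in all. It then concludes for the study: "Performing a repeat study with 75mL of intravenous contrast will not exceed the contrast dose that would have been normally administered". Section 11.0 makes the same claim without a total, and says that the usual repeat may use either a full or a reduced second dose.

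Exclusion criterion 6 in section 3.2 removes patients with GFR below 60 and adds that GFR "should be within normal range. This would allow a repeat study if needed and not pose an increased risk to renal dysfunction".

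On renal testing, section 2.3 reports a departmental policy to "evaluate renal function before a contrast enhanced CT scan in the setting of increased age (>60 years), history of renal dysfunction or diabetes". The same section lists hypertension, diabetes and older age among this population's features and comments: "All these conditions contribute to renal dysfunction". Section 2.1 adds: "In the setting of renal dysfunction, this dose is reduced to 75mL to minimize the risk of contrast induced nephropathy".

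On screening, section 4.1 says that medical records "will be evaluated prior to CTA imaging to identify subjects meeting the inclusion/exclusion criteria", and section 4.2 looks for "a prior CTA of the aorta with routine dose of intravenous contrast within the past two years". Section 5.1.1.1 states: "Informed consent will be obtained prior to examination in the IV preparation room or scanner room".

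**The concern.** Two things look wrong together. First, a reader who takes the usual dose to be the single 100 mL of section 7.4.1 will find that a study scan plus a repeat exceeds it, so the assurance in 7.2.1 appears false. Second, the acceptability of the repeat then seems to rest on criterion 6, and no section guarantees a GFR to check. The policy in 2.3 leaves out adults aged 60 or under with no renal history or diabetes. Section 7.2 lists no blood test, and consent is taken just before the scan. Read literally, an exclusion for a low value does not exclude a missing one.

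At stake would be a few subjects who receive more than one routine dose without confirmed renal function. Participation ends with the CTA (7.3), and GFR is not named among the recorded data in 7.1.

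**Working it through.** **Volumes.** Inputs: study dose 40 or 50 mL (7.1), repeat dose 75 mL (7.2.1), routine dose 100 mL (7.4.1).

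- The plan's own figure: 100 + 75 = 175 mL. It reproduces.
- Study scan plus repeat: 40 + 75 = 115 mL; 50 + 75 = 125 mL.
- Against 175 mL: 115 − 175 = −60; 125 − 175 = −50.
- Against a full second dose, as 11.0 allows (100 + 100 = 200 mL): 115 − 200 = −85; 125 − 200 = −75.
- Against one 100 mL dose: +15; +25.

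The sentence therefore holds against either repeat total and fails against a single dose. Its subject is a failed scan, and the 175 mL figure stands two sentences earlier for exactly that event. The intervening fragment, which mentions 100 mL, makes the wording loose but does not replace the comparator.

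**Criterion 6 beside the screening text.**

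- Section 3.2 applies the criterion to every patient, with no exception for those outside the policy in 2.3.
- Its second clause asks positively for a normal GFR. An absent value cannot meet that, so the reading under which a missing GFR passes uses only half the criterion.
- Section 4.1 has records checked against the criteria before imaging, and 4.4 seeks a waiver so that this can precede consent. The check does not depend on anything done in the scanner room.
- The policy in 2.3 is background. Nothing says that it is the study's only source of a GFR.
- Inclusion criterion 1 requires an earlier 100 mL scan, whereas 2.1 gives 75 mL for renal dysfunction. This is a partial safeguard only, since 4.2 lets that scan be up to two years old.

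**How many subjects.** Let m be the share of subjects with no GFR on record and r the repeat rate. The documents give neither; the values below are assumptions, and multiplying them treats the two as independent.

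| m | r | No GFR: 180 × m | No GFR and repeated: 180 × m × r |
|---|---|---|---|
| 0 | any | 0 | 0 |
| 5% | 2% | 9 | 0.18 |
| 20% | 5% | 36 | 1.8 |
| 40% | 10% | 72 | 7.2 |

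The only information on r is the technologists' remark in 2.2 that repeats are rare, and that concerns standard-dose scans.

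**Cost of a stricter rule.** If patients without a GFR were not enrolled, the otherwise eligible patients needed for 180 subjects would be 180 / 0.95 = 189.5, rounded up to 190; 180 / 0.80 = 225; or 180 / 0.60 = 300. Testing them instead would add a procedure before the scan.

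**The case for a change.** The best case for a change starts from section 2.2. If repeats are rare in routine care, most patients would normally receive 100 mL once. A subject whose scan fails only because the dose was reduced then gets 15 or 25 mL more than routine care would have given, and the 175 mL comparator does not describe that person. For that subject the GFR criterion carries the argument, and 3.2 itself says that it was written to permit a repeat. Yet the source of the GFR, its maximum age and the handling of a missing value are unwritten, the normal range is undefined beside the limit of 60, and GFR is not listed for REDCap. Writing this down would take a few lines.

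Much of this is accurate. The excess over a single dose is real for such a subject, the comparator is unnamed, and the verification details are absent. Three parts do not stand:

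- The repeat does not rest on criterion 6 alone; 7.2.1 and 11.0 also defend it on volume.
- A conflict between two GFR limits is not established. The character joining the clauses looks like a dash altered in text extraction, and the second clause can be read as explaining the first.
- The check would not be invisible afterwards. A GFR used for screening stays in the medical record, 10.4 includes data collected at screening, the list in 7.1 is illustrative, and 20.1 opens source documents to audit.

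That hypertension does not trigger testing is a comment on departmental policy, not on this protocol.

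**Conclusion.** No change to the plan follows. The statement in 7.2.1 is correct against the failed-and-repeated routine scan (115 or 125 mL against 175 mL), and loosely worded because it does not say so. Criterion 6 covers all patients and is checked from records before imaging. What is left unwritten is operational detail that screeners would sensibly supply by requiring a GFR on record before enrolling a patient.

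This conclusion rests on two readings: that the usual total in 7.2.1 means the repeat pathway, and that a missing GFR does not satisfy criterion 6. If the second failed in practice, the subjects both unverified and repeated would number about 0.2 to 7 of 180 under the assumed rates, and none if every subject has a GFR. Each would be 15 or 25 mL above one routine dose. The comparison of image quality, the 7.5% margin and the sample size are unaffected either way. Nothing here judges what GFR limit or contrast volume is appropriate; that is for the sponsor.
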